
To assess the potential effects of sirolimus on brain neuroimaging and retinal biomarkers in patients with MSA
	
Brain magnetic resonance changes using dedicated algorithms to evaluate rate of change in diffusivity of defined areas of brain from baseline to 48 weeks in patients receiving sirolimus compared to the progression of putaminal diffusivity reported in longitudinal studies of MSA.
	
Increased putaminal diffusivity has been consistently reported, even in early disease stages of MSA (42, 55-59). Increase in putaminal diffusivity has been reported to be a sensitive neuroimaging measures of disease progression in patients with MSA and has been used previously as neuroimaging

OBJECTIVES	ENDPOINTS	JUSTIFICATION FOR ENDPOINTS
	
Changes in retinal nerve fiber layer (RNFL) using optical coherence tomography from baseline to 48 weeks in patients receiving sirolimus compared to the rate of progression in longitudinal studies of MSA.
	
outcome measure in previous clinical trials of MSA (41, 42).
 
The use of optical coherence tomography (OCT) is emerging as a non-invasive fast technique to measure the thickness of the retinal layers. Even though patients with MSA only rarely have visual complaints, recent studies by our group using OCT showed that the retina of patients with MSA have consistent atrophy of the peripapillary retinal nerve fiber layer (RNFL) and to a lesser extent the macular ganglion cell layer (GCL) complex (13). These abnormalities are progressive overtime and have been recently confirmed by pathological examination in the retinas from three patients with MSA (12, 14).

Tertiary/Exploratory		

To explore the effects of sirolimus on blood biomarkers (exosomal alpha-synuclein particles) in patients with MSA
	
Change from baseline to week-48 in exosomal alpha-synuclein particle concentration in plasma in patients taking sirolimus versus the placebo group
	
The concentration of exosomal alpha-synuclein particles in plasma has been proposed as a biomarker of diagnosis of synucleinopathies. We hypothesize that sirolimus will increase autophagy and, therefore, the degradation of these exosomal alpha-synuclein particles.

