This study will include a placebo group in 3:1 proportion. Our reason for including a placebo arm is to facilitate blinding to treatment assignment and also to permit a descriptive assessment of the validity of the assumed change in UMSARS over time in the historical control group; the placebo group *will not* be used for primary outcome purposes with the active treatment arm.

This will be single-center study performed at the NYU Dysautonomia Center, one of the leading centers in the diagnosis and management of MSA. [name], the director of the Center, is the PI of the international Natural History Study of MSA, within the NIH-funded Rare Diseases Autonomic Disorders Consortium. NYU has the infrastructure and personnel in place to undertake this study and is experienced in the conduct of clinical trials. NYU is in a position to rapidly commence the study and conduct the study efficiently. We will review the option of adding additional sites if recruitment in the first 15 months is slow. Our aim is to complete recruitment within 24 months from commencement of the study.

Eligible participants, who signed the approved informed consent form at the screening visit, will initially receive sirolimus 2 mg/day (one 2-mg capsule/day) or matching placebo in a 3:1 fashion. The dose of sirolimus will be adjusted throughout the trial based on sirolimus blood levels and the presence of drug-related adverse events. The maximum dose of sirolimus will be 6 mg/day (three 2-mg capsules/day) or matching placebo. Patients receiving placebo will undergo analog sham level measurements and the number of capsules will be also adjusted to maintain the blinding of the trial. Patients will receive active agent or placebo for 48-weeks.

Participants will be evaluated at study clinic by the investigator at the screening visit and at baseline visit and will return to the clinic at Day 84 (month 3), Day 168 (month 6), Day 252 (month 9), and Day 363 (month 12) (+/- 10 days) of beginning the study treatment.

Detailed study plan

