Participants will be dispensed study medication during the baseline visit. In case this is not possible, participants will be mailed the study medication within 30 days of the baseline visit.

The case report forms will note the date when the subject will start the study medication.

Participants will also undergo a non-contrast brain MRI with specific sequences to evaluate the diffusion at the putamen and pons. The brain MRI will be performed at the NYU Center for Biomedical Imaging. There will be a brain MRI period of up to 7 days after the baseline visit (i.e., subjects must be scanned within 7 days after the baseline visit).

Scheduled site visits: assessment of the primary outcome measure and safety labs will be conducted on-site at study visits at Visit 8 (month 3 after initiation of study drug), Visit 11 (month 6 after initiation of study drug), Visit 14 (month 9 after initiation of study drug), and Visit 17 (month 12 after initiation of study drug) (+ 15 days). We will accept a visit window of 15 days after the target date. The following tasks will be performed:

- EKG
- Concomitant medications
- Adverse event recording
- Physical exam
- Vital signs
- UMSARS scale
- CBC, CMP, CPK (8 ml of blood) and urinalysis with 24-hour urine collection
- Lipid panel
- Sirolimus levels in blood (5 ml of blood)
- Retrieve study drug
- Dispense study drug. If dispensation of study drug is not possible during the visit, the study drug will be mailed within 15 days.

Safety Laboratory Visits: Assessment of safety will be conducted on-site or locally at study visits 7 days (with a window of 3 days after the target date) after initiation of study drug (Study Visit 3), and 7 days after the patient has increased dose of study drug (i.e., Study Visit 4, Study Visit 5 and Study Visit 6, with

a window of 3 days after the target date) during the first month of study drug treatment. We will accept a visit window of 3 days after the target date of these visits.

Assessment of safety visits will also occur on-site or locally on Month 2 (Study Visit 7, this visit may be skipped in previous visits were delayed, to ensure that Visit 8 occurs at Month 3), Month 4 (Study Visit 9), Month 5 (Study Visit 10), Month 7 (Study Visit 12), Month 8 (Study Visit 13), Month 10 (Study Visit 15), and Month 11 (Study Visit 16). We will accept a visit window of 15 days before or after the target date of these visits.

The following safety laboratory assessments will be performed:

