4.2 SCIENTIFIC RATIONALE FOR STUDY DESIGN

To determine whether to test sirolimus in a large phase 3 trial, we propose to conduct a clinical trial of sirolimus in MSA using a futility design. This approach minimizes the number of subjects and resources required for the study and provides an indication of whether or not to pursue larger and more definite studies. A futility design (60) is highly appropriate for MSA given: a) the low prevalence of the disease; b) the availability of historical controls from recent large studies (8, 39); and c) the availability of sensitive outcome measures. A futility design under the null hypothesis assumes that sirolimus will slow the progression of the disease, whereas the alternative hypothesis assumes no benefit of sirolimus. If the null hypothesis is rejected (i.e., futility of sirolimus to slow progression of MSA), a major phase III study will be discouraged, whereas non-futility will offer strong support for a phase III trial to detect clinical efficacy.

This study will also include a placebo group in 3:1 proportion. Our reason for including a placebo arm is to facilitate blinding to treatment assignment and also to permit a descriptive assessment of the validity of the assumed change in UMSARS over time in the historical control group; it will not be used as a basis of comparison for the active treatment arm.

This placebo-controlled futility design comparing outcome measures to historical controls has been used in other neurodegenerative disorders (61-63).

The study population (n=42 active agent, n=14 placebo) was selected based on power analysis calculation using the known annual progression of the UMSARS total score from published natural history studies (8, 39) and the progression in the placebo group of previous clinical trials of MSA(40), as well as from the minimally clinically significant difference in UMSARS (38) (see statistical section).

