model parameters for the mean diffusion of water (the apparent diffusion coefficient, or “ADC”), the degree of diffusion orientation dependence (fractional anisotropy, or “FA”) and the dominant orientation of water diffusion in an individual image voxel (first Eigen vector). In most neurodegenerative conditions, the tissue environment sampled by water becomes less organized over time and this is reflected by increasing ADC and decreasing FA. Compared to PD, increased putaminal ADC in MSA-P has been consistently reported, even in early disease stages (42, 55-59). Putaminal ADC changes have been reported to be a highly sensitive MRI marker of disease progression in patients with MSA and has been used previously as neuroimaging outcome measure in previous clinical trials of MSA (41, 42).

MRI will be carried out with a state-of-the-art 1.5-T MRI system and 24-channel head coil (Aera, Siemens Healthcare, Erlangen, Germany) – note, while 3-T has some signal-to-noise advantages, many MSA patients have cardiac pacer wires that make 3-T imaging difficult or impossible to obtain routinely. First a volumetric 3D T1-weighted MR-RAGE (TR/TE/TI 10/2/600 ms) and volumetric 3D SPACE FLAIR MRI sequences will both be obtained with 1-mm isotropic resolution (10 minutes total). Routine 3D susceptibility-weighted imaging will be obtained (5 min). Finally axial high-angular resolution diffusion MRI will be obtained of the whole brain using 3-mm isotropic resolution using echoplanar imaging, parallel imaging and 2-slice acceleration with simultaneous multi-slice acquisitions (TR/TE = 7000/100 ms, b = 0 and 1500 s/mm², 30 gradient directions). These data will be analyzed with inline scanner diffusion tensor model and parameter maps of ADC, FA and fiber orientation generated. These will be co-registered with the volumetric data and manual regions-of-interest drawn to include the entire left and right putamen to extract mean ADC and FA. A secondary neuroimaging aim in this study will be to determine whole brain, cortical, white matter and individual structure volumes at baseline and after 48 weeks using automated FreeSurfer analysis as described in the literature (67).

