$H_0: \theta_E \leq 4.6$ points increase at week 48 from baseline

$H_1: \theta_E > 4.6$ points increase at week 48 from baseline

Therefore, assuming an alpha of 0.05, and a power of 0.8 (one sided, as patients with MSA have not been reported to improve spontaneously) to detect a progression of 4.6 points (i.e., 8.6 minus 4) in the UMSARS total score after 48-weeks from baseline we will need to enroll 38 patients in the active agent arm. Anticipating a 10% for dropouts rate, we will need to enroll 42 patients in the active agent arm.

This trial will include a placebo group to facilitate blinding in a 3:1 proportion. However, statistical comparisons for the primary and secondary efficacy outcome measures will be performed between the active agent arm and the historical controls. We will therefore enroll 14 patients in the placebo arm.

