9.4.6 SUB-GROUP ANALYSES

Not applicable

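### The MRI and OCT secondaries are tested only against undocumented published rates; a supportive sirolimus-minus-placebo estimate from scans already planned should be added.

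*Combined protocol and SAP*

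**What the plan says.** Section 3 defines the MRI endpoint as change in sirolimus patients "compared to the progression of putaminal diffusivity reported in longitudinal studies of MSA", and words the OCT endpoint in the same way. Section 9.1 sets the thresholds: 0.03 for Trace(D), which is 0.04 below the historical 0.07, and 1.45 µm for RNFL thinning, which is 2.25 below the historical 3.7. Section 9.4.3 analyses each by a one-sample t-test in the sirolimus arm. Section 9.2 confirms that "statistical comparisons for the primary and secondary efficacy outcome measures will be performed between the active agent arm and the historical controls".

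On the placebo arm, section 4.2 says "it will not be used as a basis of comparison for the active treatment arm". Its one stated analytic role, in section 4.1, is "to permit a descriptive assessment of the validity of the assumed change in UMSARS over time in the historical control group"; imaging is not mentioned. Sections 1.2 and 4.1 give both arms the same MRI and OCT at baseline and end of study. The plan does compare sirolimus with placebo elsewhere: for exosomal alpha-synuclein (sections 3 and 9.4.3) and in the interim criteria (section 9.4.5).

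On subtype, both MSA-P and MSA-C are eligible (section 5.1) and randomisation is stratified by MSA type (section 6.3). Section 9.4.3 has no adjustment for it, and section 9.4.6 on subgroups reads "Not applicable". Section 4.1 describes a "non-contrast brain MRI with specific sequences to evaluate the diffusion at the putamen and pons", but section 8.1 draws diffusion regions only in the putamen. Section 8.1 supports the marker partly with MSA-P evidence: "Compared to PD, increased putaminal ADC in MSA-P has been consistently reported, even in early disease stages".

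**The concern.** A one-sample test against a constant attributes every departure from that constant to treatment. For UMSARS the plan documents its constant: section 9.2 names two cohorts (n=96 and n=50) with means, SDs and a pooled value. For 0.07 and 3.7 it gives only a citation. Differences in scanner, sequence, region drawing or patient mix between this trial and the published series therefore go straight into the apparent drug effect. Section 8.1 itself extracts ADC and FA while sections 9.1 and 9.4.3 test Trace(D), so the measured quantity and the constant are not shown to be on one scale.

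The placebo scans come from the same machines, readers and recruitment, with MSA type balanced by stratification. Offsets shared by both arms cancel, in expectation, in the difference between arms. What is at stake is how the stated secondary objective, the effect of sirolimus on brain and retinal imaging, can be interpreted.

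**Working it through.** **The plan's own figures.** 0.07 − 0.04 = 0.03 and 3.7 − 2.25 = 1.45; both thresholds reproduce. The plan states no SD, sample size or power for MRI or OCT.

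**How large an offset would matter.** An inert drug sits on the threshold if the untreated rate here is lower than the published one by 0.04/0.07 = 57% (MRI) or 2.25/3.7 = 61% (OCT). Smaller offsets erode the test in proportion.

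**Case-mix illustration, MRI only.** Assumptions, none of them established by the documents: 0.07 is an MSA-P rate; the MSA-C share f is 20–33% (from the 2:1 to 4:1 ratio in section 2.1, which describes most countries, not this trial); MSA-C putaminal change is r × 0.07 with r from 0 to 0.5.

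Untreated mean = 0.07 × [(1 − f) + f × r]; offset = 0.07 minus that mean.

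| f | r | Untreated mean | Offset | Share of 0.04 |
|---|---|---|---|---|
| 0.20 | 0.5 | 0.063 | 0.007 | 18% |
| 0.33 | 0.5 | 0.058 | 0.012 | 29% |
| 0.20 | 0 | 0.056 | 0.014 | 35% |
| 0.33 | 0 | 0.047 | 0.023 | 58% |

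If r = 1, or if the published series had the same mix as this trial, the offset is zero. If that series had more MSA-C than this trial and r is below 1, the sign reverses.

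**Effect on the planned test.** One-sample t-test against 0.03, n = 38, one-sided 0.05, noncentrality (0.04 − offset) × √38 / SD. The SD is assumed. The chance of finding futility for an inert drug is:
- SD 0.08: 92% with no offset, then 80%, 69%, 63% and 35% at the four offsets above.
- SD 0.05: 99.9% with no offset, then 99%, 96%, 93% and 65%.

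**Precision of the placebo contrast.** After 10% dropout, 42 × 0.9 = 37.8 (about 38) and 14 × 0.9 = 12.6 (about 13).
- One-sample SE = SD × √(1/38) = 0.16 SD.
- Two-arm SE = SD × √(1/38 + 1/12.6) = 0.33 SD.
- Detectable difference, one-sided 0.05, 80% power: (1.645 + 0.842) × 0.325 = 0.81 SD, against 0.40 SD for the one-sample test.
- With the full 42 versus 14, power for 0.04 is 83%, 49% and 36% at assumed SDs of 0.05, 0.08 and 0.10. For 2.25 µm it is 78%, 57% and 43% at assumed SDs of 3, 4 and 5.

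**Bias against variance.** One-sample mean squared error is bias² + SD²/38; for the two-arm contrast it is SD²/38 + SD²/12.6. They are equal when bias = SD × √(1/12.6) = 0.28 SD, that is 0.014, 0.023 or 0.028 at assumed SDs of 0.05, 0.08 or 0.10.

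**The case against.** The historical-control futility design is declared and given precedents in section 4.2, and the placebo arm was sized for blinding. Imaging sits below UMSARS in a gated hierarchy, and the phase III decision rests on UMSARS (section 4.1). On the last calculation above, the placebo contrast is the more accurate estimate only if bias exceeds about 0.28 SD, and most of the illustrated case-mix range is below that at SDs of 0.08–0.10. All of this stands, and it is why the historical tests should stay.

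Four stronger readings are tempting and are not supported:
- A reader might infer that MRI is known to be biased toward benefit by up to 58%. The documents do not say that 0.07 is an MSA-P rate or that MSA-C change is smaller. Section 9.1 attributes 0.07 to studies of MSA, and sections 3 and 8.1 also support the putaminal marker for MSA generally.
- A reader might carry the subtype argument over to OCT. Nothing in the documents ties RNFL change to subtype. Section 8.1 describes the earlier OCT work as the group's own, so a device difference behind 3.7 is possible but not shown.
- A reader might call sirolimus minus placebo the one unbiased estimate and want it to replace the historical test. Section 9.3 restricts analysis to patients completing three months of drug, which is selection after randomisation, and the contrast is imprecise.
- A reader might conclude that the imaging objective cannot be met. The limitation lies in the listed tests; the data to do better are collected.

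What the objection does not answer is why scans collected identically in the placebo arm have no planned use, when placebo is already compared for exosomes and at the interim.

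**Conclusion.** The concern holds in a limited form. As planned, the MRI and OCT tests cannot distinguish a drug effect from a difference between this trial and published series whose SD, acquisition method and subtype mix the plan does not give. The 0.007–0.023 figure shows what case mix could do to MRI under stated assumptions; it is not an estimate of actual bias. Bias from scanner or region drawing cannot be sized from the documents for either modality. The primary futility decision is unaffected. Adding a supportive estimate is a cheap improvement; replacing the historical comparison is not warranted.

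**What to change.** Keep the one-sample tests and their place in the hierarchy. Then:
- Add to section 9.4.3 a prespecified supportive estimate, outside the testing hierarchy: the sirolimus-minus-placebo difference in 48-week change in putaminal diffusivity and in RNFL, with a 95% CI, adjusted for baseline value and MSA type. Use all randomised patients with imaging, not only those completing three months of drug.
- Report mean placebo change with its CI beside 0.07 and 3.7, as a check on those constants, matching what is already intended for UMSARS.
- Tabulate MRI change by MSA type, descriptively only: at a 20–33% share, the placebo arm would hold about 14 × 0.20 = 3 to 14 × 0.33 = 5 MSA-C patients.
- State the SD, acquisition method and subtype mix behind both constants where the sources give them, and reconcile ADC in section 8.1 with Trace(D) in sections 9.1 and 9.4.3.
- Amend the sentence in section 9.2, and the matching text in sections 3 and 4.2, to allow this.

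A pontine diffusion measure from the same scans is optional. The cost is some extra analysis, with no new scans, visits or patients. The interval will be wide: about ±1.96 × 0.325 = ±0.64 SD. It should be presented as estimation.

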9.3 POPULATIONS FOR ANALYSES

Analyses will be performed according to the intention-to-treat principle and will include all randomized subjects who have completed, at least, 3 months of study drug.

